Protocol deviations will be defined as noncompliance with the research protocol that does not increase risk or decrease benefit and/or affect the integrity of the data. Protocol deviations may result from the action of the participant, research staff, or MR Facility and MR staff. All protocol deviations will be documented on a participant-specific Protocol Deviation Form and will explain any deviation from the approved protocol. Protocol

deviations will be reported to the IRB and NIMH PO by the PI with the continuing review and annual progress report, respectively.

Adverse Events (AEs) are defined as any untoward or unfavorable medical occurrence in a human participant, including any abnormal sign (for example, abnormal MRI finding), symptom, or disease, temporally associated with the participant's participation in the research, whether or not considered related to the participant's participation in the research. Study personnel will ask each participant about the presence/absence of adverse events (AEs) at every study visit and document AE presence/absence. AEs will be documented in a participant-specific AE log, which will include documentation of the following information: a) grading the AE as mild, moderate, or severe; b) determining how likely the AE is related to the participant's participation in the study procedures; c) action taken regarding study participation; d) outcome of the AE; e) whether the AE was expected or unexpected (not listed as a potential side effect/risk in the protocol); and f) whether the AE is determined to be a serious adverse event (SAE).

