A serious adverse event (SAE) is any severe adverse experience occurring during the study that: (a) results in death, (b) is life-threatening (e.g., suicidality, homicidality), (c) results in hospitalization or prolongation of existing hospitalization, (d) results in persistent or significant disability, (e) is a congenital anomaly or birth defect, or (f) any other AE that, based on appropriate medical judgment, may jeopardize the subject's health and may require medical or surgical intervention to prevent one of the other outcomes listed in this definition. Moderate AEs are defined as any non-serious event which causes discomfort and requires treatment, but does not pose any significant or permanent risk of harm to the participant or require in-patient hospitalization, including social or psychological trauma causing moderate or temporary distress, significant embarrassment, stigmatization of individual or community/ group, disruption of familial/social relationships or nontrivial emotional distress. Moderate AEs will include evaluation in the emergency room not leading to hospitalization. Mild is defined as any non-serious event of less than moderate severity. All SAEs and unexpected AEs will be reported to the PI or Co-Is [name] or [name] as soon as possible within 24 hours of the study staff becoming aware of the S/AE. The PI or Co-Is [name] or [name] will determine whether participation in the study should be altered or terminated for the safety of the participant.

All unexpected problems, defined as any incident, experience, or outcome that is **unexpected, related or possibly related** to participation in the research, and suggest that the research places participants are **greater risk of harm than was previously known or recognized** will be reported by the PI to the IRB and NIMH PO as soon as possible, but within 5 business days of the PI becoming aware of the AE. For all AEs and SAEs that are deemed expected and/or unrelated to the study, a summary will be submitted by the PI to the NIMH PO with the annual progress report.

Documentation of protocol deviations will begin at Visit 1 and documentation of AEs will begin once a participant begins Visit 3 and will be collected/document until the participant completes the study procedures (at the end of Visit 5) or is withdraw from the study (by self or my research staff).

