Weekly meetings of the research staff of this study will be conducted that will include review of accrual, consenting procedures, protocol adherence, AEs, and quality control of all data obtained from the study in the previous weeks. Minutes of these meetings will be recorded, signed by the PI, and archived in a Regulatory Folder on the lab server. In addition, to participant-specific protocol deviation forms, protocol deviation will also be documented in a study-wide deviations log to facilitate monitoring and reporting to regulatory authorities. Similarly, AEs will be also documented in a study-wide AE log, which will be used to facilitate safety monitoring and identify AE trends across subjects, as well as overall AE reporting to the IRB and NIMH.

We will conduct a preliminary analysis during the early stages of data collection (once \approx 10% of the THC group has completed the study) to assess the efficacy and safety of the 5mg and 10mg doses and submit an amendment to adjust the dosing as needed (e.g. if 10mg shows significant improvement over 5mg, a further

increase in dosing [15mg] would be worthwhile). Our efficacy and safety metrics are based on the following criteria:

- 1) a. At least a medium effect size (Cohen's $d \geq 0.05$) between THC and PBO conditions in BOLD responses in *a priori* ROIs (vmPFC and/or HPC) and/or peripheral measures (SCR, US expectancy, SUDS) during recall of extinction learning; or
 - b. Relationship between change in BOLD responses in *a priori* ROIs (vmPFC and/or HPC) and/or change in peripheral measures (SCR, US expectancy, SUDS) during recall of extinction learning in THC (vs. PBO) is of at least a medium effect size ($r \geq 0.30$).
- 2) There will be no adverse events of more than mild severity that are rated as possibly, probably, or definitely related to acute administration of THC (more than PBO) in PTSD participants.

We will apply O'Brien-Fleming¹⁷⁹ type monitoring bounds as guidelines for the decisions regarding continuation or early termination of the trial. In addition to efficacy comparisons, frequency of AEs along with formal statistical comparisons of the frequency of AEs will be performed.

Reporting responsibility

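### The safety plan does not clearly require prompt outside notice of a study-related SAE whose event type the protocol already lists

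*Combined protocol and SAP*

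**What the plan says.** All of the reporting rules stand in section 5, Data and Safety Monitoring Plan, of the combined protocol and SAP.

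- **Classification.** The AE log records relatedness under item (b), "determining how likely the AE is related to the participant's participation in the study procedures", and expectedness under item (e), "whether the AE was expected or unexpected (not listed as a potential side effect/risk in the protocol"). An SAE is defined mainly by outcome; hospitalisation is one of the qualifying outcomes.
- **Internal report.** "All SAEs and unexpected AEs will be reported to the PI or Co-Is" within 24 hours of staff becoming aware.
- **Prompt outside report.** This covers unexpected problems, "defined as any incident, experience, or outcome that is" unexpected, related or possibly related, and suggestive of more risk than was previously recognised. The PI reports these to the IRB and NIMH PO "as soon as possible, but within 5 business days of the PI becoming aware of the AE".
- **Annual report.** The other written route reads, in part, "AEs and SAEs that are deemed expected and/or unrelated to the study, a summary will be submitted by the PI to the NIMH PO". It falls due once a year, together with the progress report.
- **Study-wide log.** It supports safety monitoring and trend detection, "as well as overall AE reporting to the IRB and NIMH". No deadline is attached.

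Section 1.c, Potential Risks, under Dronabinol, lists panic attacks, paranoid reaction and confusion among effects with an incidence of 1%-10%. It sets no severity limit on any of them.

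**The concern.** Expectedness decides whether an outside body hears of an event within days or within the year. The plan's only definition of it asks whether the event type is on a list, not how severe the event is. Several listed dronabinol effects could, in a bad case, put a participant in hospital. Such an event would be serious and could be drug-related, and it would still qualify as expected.

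What is at stake is timely outside oversight. The IRB and NIMH PO are the outside bodies the plan names for AE reports, and the documents name no data and safety monitoring board or independent medical monitor. The PI holds ultimate responsibility for event reporting (Reporting responsibility) and also dispenses the study drug (Study Group Assignment). Prompt outside notice therefore depends on a classification made inside the study team. Section 5 also foresees an early look at the data that could lead to a 15 mg dose, a point at which outside bodies should already know of any related serious event.

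**Working it through.** No figure in the plan needs to be reproduced and no arithmetic applies. The check follows one case through the written rules: a panic attack or paranoid reaction, rated related to dronabinol, that leads to hospitalisation.

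1. **Is it serious?** Yes. Hospitalisation is one of the SAE outcomes in section 5.
2. **Is it listed?** Yes. Both effects appear in section 1.c, Dronabinol, without a severity limit.
3. **Is it expected?** Under log item (e), yes, because the item asks only about listing.
4. **Who hears within 24 hours?** The PI or Co-Is, who belong to the study team.
5. **Is the 5-business-day outside report triggered?** Its three conditions (unexpected, related or possibly related, suggestive of greater risk) apply jointly. If item (e) governs the word unexpected, the first condition fails, and the greater-risk condition cannot bring the event back in by itself.
6. **What outside route remains?** The annual summary. It covers events deemed expected and/or unrelated, so being expected is enough even for a related SAE. The timing moves from 5 business days to as much as about 12 months, depending on when the event falls between annual reports.
7. **Who receives it?** The NIMH PO is named and the IRB is not. By contrast, protocol "deviations will be reported to the IRB and NIMH PO by the PI with the continuing review and annual progress report, respectively", although section 5 defines a deviation as noncompliance that does not add risk.
8. **Does another rule fill the gap?** The study-wide log mentions the IRB and NIMH without a deadline. The second criterion of the early analysis in section 5 calls for no THC-related AE above mild severity, listed or not. That is a partial control: it applies once about 10% of the THC group has completed, and it names no outside recipient.

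The result depends on step 5. If the PI reads unexpected more broadly than item (e), the prompt report can be made. The text allows that reading but does not require it.

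**The case against.** The strongest reply is that item (e) only describes a log field. The 5-day rule has its own subject, "defined as any incident, experience, or outcome that is" unexpected, and does not refer back to the log. No section lists hospitalisation as an expected outcome of dosing. Study Group Assignment says that 10 mg does not typically cause anxiety, and section 3 describes the burden on participants as passing discomfort. Against that background, a drug-related hospitalisation is naturally an unexpected outcome that suggests greater risk. This stands as a permitted reading, and it is why the point says *not clearly required*. It does not close the gap, because item (e) is the only definition of unexpected in the plan and the annual route is written to include SAEs.

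The internal controls are also real. They include the 24-hour report, Co-I consultation on grading, weekly AE review, a single dose with a physician on site or on call, planned AE-frequency comparisons and O'Brien-Fleming type bounds. They lower the risk to participants, but none gives an outside body dated notice of such an event. IRB or funder policy may already require prompt reporting; that cannot be checked from these documents.

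Three stronger inferences are tempting and are not supported:

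- A reader might infer that deaths or suicidality could be held for the annual summary as expected drug effects. Neither is among the listed dronabinol effects, so both can already count as unexpected.
- A reader might infer that the IRB is shut out of AE reporting. The log wording names the IRB; what is missing is a deadline and a rule specific to SAEs.
- A reader might extend the point to serious MRI injuries because section 1.c lists them too. The MRI safeguards in section 2.b mean such an injury would imply that those safeguards had failed, so calling it expected is strained. The point does not rest on it.

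**Conclusion.** The concern holds in a limited form. For a study-related SAE of a listed type, the plan does not clearly require prompt notice to the IRB or NIMH PO, and its literal wording allows an annual summary to the NIMH PO alone. The gap is confined to listed event types and to the case where the PI applies item (e) as written.

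Its practical size is unknown. The documents give no SAE rate, and the 1%-10% incidence for the listed dronabinol effects is not a rate of serious events. A reader might infer that a large share of related SAEs would escape prompt reporting; nothing in the documents supports any such share. The conclusion assumes that no outside policy overrides the plan. It is a low-priority improvement to consider; it does not affect the design, sample size or efficacy analysis.

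**What to change.** Make two edits in section 5.

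1. In log item (e), define unexpected as not listed in the protocol by nature, severity or frequency, and state that no listed effect is expected at a serious level.
2. In the reporting paragraph, send every SAE rated related or possibly related to the capsule or to any study procedure, in any group including the trauma-exposed controls, to the IRB and NIMH PO within the existing 5 business days, whether expected or not. Leave the 5-day rule for other unexpected problems as it is. Keep the annual summary for unrelated SAEs and expected non-serious AEs.

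The cost is a few sentences. Recipients and deadline already exist, and relatedness is already rated under item (b). There may be a few more expedited reports; without an SAE rate the number cannot be stated. Rating relatedness will still take judgement, but the expectedness and greater-risk calls would no longer decide whether a related SAE is reported promptly.

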Discovery and disclosure of incidental finding or abnormality on MRI scans: During the formal consent process, all participants will be informed about the potential risks of discovering an incidental finding or abnormality on their MRI scan. If an abnormality is found in a participant's MRI scan, the PI may ask a radiologist at the MR Facility will review the scan data and provide recommendation to the PI if the incidental finding or abnormality is something the participant should follow-up with their primary care physician about. If follow-up is recommended, the PI will contact the participant. The decision as to whether to proceed with further examination and/or treatment lies solely with the participant and his/her primary care physician.

Dronabinol

Dronabinol is associated with some adverse experiences (incidence 1%-10%) including: asthenia, increases in heart rate, palpitations, facial flush, sensory impairment, headache, nausea, vomiting, dry mouth, changes in appetite, easy laughing, euphoria, restlessness, panic attacks, anxiety/nervousness, paranoid reaction, confusion, dizziness, drowsiness, and impairment in coordination. A board-certified psychiatrist and/or physician associated with the study (Co-I [name] or Co-I [name]) or his/her physician designate, will be available during all behavioral tasks and pharmacological challenge days to evaluate and recommend further evaluation and treatment for the emergence of any adverse events/side effects.

Participants taking medications that have level 1 evidence indicating severe drug-drug interaction with dronabinol daily will be excluded. Also, we will exclude participants with a known sensitivity to the active drug or capsule excipients, including cannabinoid oil, sesame oil, gelatin, glycerin, and titanium dioxide. Pregnant participants will be excluded from participation because there is insufficient data to assure safety of the fetus during dronabinol exposure, as well as during MR scanning. In addition, nursing mothers will be excluded from the study because dronabinol is concentrated in and secreted in human breast milk and is absorbed by the nursing baby (for reference see: <http://www.fda.gov/ohrms/dockets/05n0479/05N-0479-emc0004-04.pdf>).

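### AE grading leaves severe undefined and rests moderate mainly on need for treatment, so intense untreated reactions may be graded mild and miss the safety criterion

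*Combined protocol and SAP*

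**What the plan says.** The rules are in the combined protocol and SAP, Protection of Human Participants, section 5 (Data and Safety Monitoring Plan).

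- **AE log.** Item (a) is "grading the AE as mild, moderate, or severe". SAE status is a separate item, (f).
- **SAE.** "A serious adverse event (SAE) is any severe adverse experience occurring during the study" that also meets one of outcomes (a) to (f). Hospitalisation is (c), and (f) is a medical-judgement route.
- **Moderate.** "Moderate AEs are defined as any non-serious event which causes discomfort and requires treatment". The same sentence caps the grade: the event must carry no significant or lasting risk of harm and need no admission. It then lists psychological trauma and emotional distress beyond the trivial as included. A further sentence adds emergency-room assessment without admission.
- **Mild.** "Mild is defined as any non-serious event of less than moderate severity".
- **Severe.** Not defined. In section 5 the word appears only in the list of grades and in the opening of the SAE definition.
- **Safety criterion 2.** "There will be no adverse events of more than mild severity that are rated as possibly, probably, or definitely related" to THC, with a parenthetical comparison to placebo. It is one of the metrics for the preliminary analysis, done when about 10% of the THC group has finished, which may lead to a dosing amendment.

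Under Potential Risks, Dronabinol, the plan gives an incidence of 1%-10% for a list of effects that includes "panic attacks, anxiety/nervousness, paranoid reaction, confusion, dizziness", as well as palpitations and vomiting.

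**The concern.** Criterion 2 depends entirely on the boundary between mild and moderate, and the plan draws that boundary mainly by whether treatment was needed, not by how bad the event was. A single oral dose can produce a reaction that is intense, ends a session and then wears off. The plan foresees something close to this: under Protection Against Risk, Magnetic Resonance Imaging, an anxious reaction in the scanner leads to stopping the session and watching the participant. If such a reaction needs no treatment, the lead test for moderate is not met.

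Two things are at stake. First, the criterion that informs the dosing decision may be recorded as met although participants had marked reactions. Second, SAE status affects reporting. SAEs and unexpected AEs go to the PI or Co-Is within 24 hours. The listed dronabinol reactions are expected by the plan's own definition, so a listed reaction that is not classed as an SAE does not trigger that report.

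**Working it through.** The plan states no figure for the AE grades or for how criterion 2 will behave, so there is nothing to reproduce. The check is to run four kinds of event through the definitions.

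1. **Intense palpitations, vomiting or dizziness, no treatment needed.** The lead test for moderate fails for want of treatment. The distress wording does not naturally cover somatic events. Severe has no definition to apply. Mild takes what is left, if *less than moderate* is read against the definition of moderate just given. Result: may be graded mild.
2. **Panic, anxiety or paranoid reaction, no treatment needed.** If the listed distress examples widen the treatment test, the event is moderate. If they remain subject to it, the event is mild. The sentence allows both readings. Result: two raters may grade the same event differently.
3. **Non-serious event with significant risk of harm.** The cap excludes it from moderate, and it is not below moderate. Severe is the only grade left. Result: no defined grade, although the label is available.
4. **Hospitalisation for an event not judged severe.** The opening of the SAE definition excludes it, the cap excludes it from moderate, and it is not below moderate. Result: read literally, no class.

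**Illustration only.** Inputs:
- THC group: 26 + 26 = 52 randomised (Nature of Participant Population). The look comes at about 10%: 0.10 × 52 = 5.2, so n = 5.
- p, the true rate of reactions that deserve a grade above mild: assumed 1%, 5% and 10%. These values borrow the any-grade range in the dronabinol risk text. The plan gives no rate for intense reactions.
- m, the share of those reactions graded mild: assumed 0, 50% and 100%.
- Assumed: every such reaction is rated related to THC, and one recorded event breaches criterion 2. The placebo parenthesis could be read differently.

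Chance of at least one recorded event above mild = 1 − (1 − p(1 − m))^n.

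| p | n = 5, m = 0 | n = 5, m = 50% | n = 5, m = 100% |
|---|---|---|---|
| 1% | 1 − 0.99^5 = 0.05 | 1 − 0.995^5 = 0.02 | 0 |
| 5% | 1 − 0.95^5 = 0.23 | 1 − 0.975^5 = 0.12 | 0 |
| 10% | 1 − 0.90^5 = 0.41 | 1 − 0.95^5 = 0.23 | 0 |

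With all 52 THC participants and p = 10%, the chance is 0.996 at m = 0 and 0.93 at m = 50%. In this illustration, partial under-grading at p = 10% matters mostly at the early look. The criterion becomes impossible to breach only if every such reaction is graded mild.

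**The case against.** A reader might infer that every intense untreated reaction is mild by definition and that criterion 2 can never be breached. The documents do not support that. Mild means below moderate *severity*, so a rater may refuse to call an incapacitating event mild. Severe is an available grade, and an event so graded is above mild. The distress wording lets untreated panic or paranoia count as moderate. Under Reporting responsibility, Co-Is are consulted on grading. Also, an event can require treatment without receiving it, so *untreated* does not by itself mean *mild*.

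Criterion 2 is not the only safeguard either. Section 5 adds weekly AE review, a study-wide AE log for trends and formal comparisons of AE frequency, none limited by grade. Heart rate, blood pressure and subjective drug effects are collected through the drug session. Nor do the documents say that drug reactions are generally observed rather than treated: a physician is to be available to recommend evaluation and treatment, and the stop-and-watch text concerns anxiety in the scanner.

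All of this stands, and it limits the point to a risk of under-grading. It does not remove the point. Consultation cannot supply a missing definition or make raters consistent. The distress wording is ambiguous and does little for somatic reactions. The other safeguards carry no stated threshold, whereas criterion 2 does. The hospitalisation gap depends on a literal reading; the plan evidently means admission to mark an SAE, and the text should say so.

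**Conclusion.** The concern holds as a defect in the definitions. Section 5 requires a severe grade that it does not define, makes need for treatment the lead test for moderate, and ties SAE status to severity although the log keeps the two apart. Intense reactions that need no treatment, somatic ones above all, may be graded mild and so fail to breach criterion 2. Untreated panic or anxiety may be graded inconsistently. On a literal reading, a hospitalisation for an event not judged severe has no class.

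No magnitude is claimed. A reader might take the top of the 1%-10% range and a full arm of 26, obtain 1 − 0.9^26 = 0.94, and conclude that such a breach would be hidden. The documents do not support this. The range covers listed effects of any grade, including dry mouth; the stated look has about 5 THC participants across both doses, not 26 per dose; and complete concealment assumes that every such event is misgraded. The conclusion rests on the wording alone, and the table above only shows how it could play out under the stated assumptions.

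**What to change.** Reconcile the AE log items, the AE and SAE definitions and criterion 2 in section 5:

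- Define mild, moderate and severe by intensity, meaning the degree of interference with the session or usual activity, independently of seriousness. State plainly how emotional distress is graded.
- Record treatment in its own field, not as a condition for moderate.
- Delete *severe* from the SAE definition, so that any AE meeting (a) to (f) is an SAE.
- State that criterion 2 applies to the intensity grade.

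This takes a few lines in the protocol and a change to the AE log, and should be in place before the preliminary look. The cost is that more events will be graded above mild, so a criterion that tolerates none may be breached more often. The sponsor should confirm, knowing this, that the threshold is still the intended one; no other threshold is proposed here.
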